### ***9.2 Source Documents***

Source data is all information, original records of clinical findings, observations, or other activities in a clinical trial necessary for the reconstruction and evaluation of the trial.

Source data are contained in source documents. Examples of these original documents, and data records include: hospital records, clinical and office charts, laboratory notes, memoranda, subjects' diaries or evaluation checklists, pharmacy dispensing records, recorded data from automated instruments, copies or transcriptions certified after verification as being accurate and complete, microfiches, photographic negatives, microfilm or magnetic media, x-rays, subject files, and records kept at the pharmacy, at the laboratories, and at medico-technical departments involved in the clinical trial.

### ***9.3 Case Report Forms***

The study case report form (CRF) is the primary data collection instrument for the study. All data requested on the CRF must be recorded. All missing data must be explained. Data will be collected using CRFs designed, stored and secured in Velos.

### ***9.4 Study Monitoring, Auditing and Inspecting***

The investigator will permit study-related monitoring, audits, and inspections by the IRB, the sponsor, government regulatory bodies, and the ACC CRU monitors of all study related documents (e.g. source documents, regulatory documents, data collection instruments, study data etc.). The investigator will ensure the capability for inspections of applicable study-related facilities (e.g. pharmacy, diagnostic laboratory, etc.). Participation as an investigator in this study implies acceptance of potential inspection by government regulatory authorities and applicable University compliance and quality assurance offices. [name] will act as medical monitor for this study.

## **10.0 MEASUREMENT OF EFFECT**

Response and progression will be evaluated in this study using the new international criteria proposed by the revised Response Evaluation Criteria in Solid Tumors (RECIST) guideline (version 1.1) [Eur J Ca 45:228-247, 2009]. Changes in the largest diameter (unidimensional measurement) of the tumor lesions and the shortest diameter in the case of malignant lymph nodes are used in the RECIST criteria.

### ***10.1 Definitions***

Evaluable for toxicity: All patients will be evaluable for toxicity from the time of their first treatment on study.

Evaluable for objective response: Only those patients who have measurable disease present at baseline, have received at least one cycle of therapy, and have had their disease re-evaluated will be considered evaluable for response. These patients will have their response classified according to the definitions stated below. (Note: Patients who exhibit objective disease progression prior to the end of cycle 1 will also be considered evaluable.)

Evaluable Non-Target Disease Response: Patients who have lesions present at baseline that are evaluable but do not meet the definitions of measurable disease, have received at least one cycle of therapy, and have had their disease re-evaluated will be considered evaluable for non-target disease. The response assessment is based on the presence, absence, or unequivocal progression of the lesions.

### ***10.2 Disease Parameters***

Measurable disease: Measurable lesions are defined as those that can be accurately measured in at least one dimension (longest diameter to be recorded) as >20 mm by chest x-ray, as >10 mm with CT scan, or >10 mm with calipers by clinical exam. All tumor measurements must be recorded in millimeters (or decimal fractions of centimeters).

Malignant lymph nodes: To be considered pathologically enlarged and measurable, a lymph node must be >15 mm in short axis when assessed by CT scan (CT scan slice thickness recommended to be no greater than 5 mm). At baseline and in follow-up, only the short axis will be measured and followed.

Non-measurable disease: All other lesions (or sites of disease), including small lesions (longest diameter <10 mm or pathological lymph nodes with  $\geq 10$  to <15 mm short axis), are considered non-measurable disease. Bone lesions, leptomeningeal disease, ascites, pleural/pericardial effusions, lymphangitis cutis/pulmonitis, inflammatory breast disease, and abdominal masses (not followed by CT or MRI), are considered as non-measurable. Note: Cystic lesions that meet the criteria for radiographically defined simple cysts should not be considered as malignant lesions (neither measurable nor non-measurable) since they are, by definition, simple cysts.

‘Cystic lesions’ thought to represent cystic metastases can be considered as measurable lesions, if they meet the definition of measurability described above. However, if non-cystic lesions are present in the same patient, these are preferred for selection as target lesions.

Target lesions: All measurable lesions up to a maximum of 2 lesions per organ and 5 lesions in total, representative of all involved organs, should be identified as target lesions and recorded and measured at baseline. Target lesions should be selected on the basis of their size (lesions with the longest diameter), be representative of all involved organs, but in addition should be those that lend themselves to reproducible repeated measurements. It may be the case that, on occasion, the largest lesion does not lend itself to reproducible measurement in which circumstance the next largest lesion which can be measured reproducibly should be selected. A sum of the diameters (longest for non-nodal lesions, short axis for nodal lesions) for all target lesions will be calculated and reported as the baseline sum diameters. If lymph nodes are to be included in the sum, then only the short axis is added into the sum. The baseline sum diameters will be used as reference to further characterize any objective tumor regression in the measurable dimension of the disease.

Non-target lesions: All other lesions (or sites of disease) including any measurable lesions over and above the 5 target lesions should be identified as non-target lesions and should also be recorded at baseline. Measurements of these lesions are not required, but the presence, absence, or in rare cases unequivocal progression of each should be noted throughout follow-up.

### ***10.3 Methods for Evaluation of Measurable Disease***

All measurements should be taken and recorded in metric notation using a ruler or calipers. All baseline evaluations should be performed as closely as possible to the beginning of treatment and never more than 4 weeks before the beginning of the treatment.

The same method of assessment and the same technique should be used to characterize each identified and reported lesion at baseline and during follow-up. Imaging-based evaluation is preferred to evaluation by clinical examination unless the lesion(s) being followed cannot be imaged but are assessable by clinical exam.

#### 10.3.1 Clinical lesions

Clinical lesions will only be considered measurable when they are superficial (e.g., skin nodules and palpable lymph nodes) and <10 mm diameter as assessed using calipers (e.g.,

skin nodules). In the case of skin lesions, documentation by color photography, including a ruler to estimate the size of the lesion, is recommended.

### 10.3.2 Conventional CT and MRI

This guideline has defined measurability of lesions on CT scan based on the assumption that CT slice thickness is 5 mm or less. If CT scans have slice thickness greater than 5 mm, the minimum size for a measurable lesion should be twice the slice thickness. MRI is also acceptable in certain situations (e.g. for body scans).

Use of MRI remains a complex issue. MRI has excellent contrast, spatial, and temporal resolution; however, there are many image acquisition variables involved in MRI, which greatly impact image quality, lesion conspicuity, and measurement. Furthermore, the availability of MRI is variable globally. As with CT, if an MRI is performed, the technical specifications of the scanning sequences used should be optimized for the evaluation of the type and site of disease. Furthermore, as with CT, the modality used at follow-up should be the same as was used at baseline and the lesions should be measured/assessed on the same pulse sequence. It is beyond the scope of the RECIST guidelines to prescribe specific MRI pulse sequence parameters for all scanners, body parts, and diseases. Ideally, the same type of scanner should be used and the image acquisition protocol should be followed as closely as possible to prior scans. Body scans should be performed with breath-hold scanning techniques, if possible.

### 10.3.3 PET-CT

At present, the low dose or attenuation correction CT portion of a combined PET-CT is not always of optimal diagnostic CT quality for use with RECIST measurements. However, if the site can document that the CT performed as part of a PET-CT is of identical diagnostic quality to a diagnostic CT (with IV and oral contrast), then the CT portion of the PET-CT can be used for RECIST measurements and can be used interchangeably with conventional CT in accurately measuring cancer lesions over time. Note, however, that the PET portion of the CT introduces additional data which may bias an investigator if it is not routinely or serially performed.

#### 10.3.4 Ultrasound

Ultrasound is not useful in assessment of lesion size and should not be used as a method of measurement. Ultrasound examinations cannot be reproduced in their entirety for independent review at a later date and, because they are operator dependent, it cannot be guaranteed that the same technique and measurements will be taken from one assessment to the next. If new lesions are identified by ultrasound in the course of the study, confirmation by CT or MRI is advised. If there is concern about radiation exposure at CT, MRI may be used instead of CT in selected instances.

#### 10.3.5 Tumor markers

Tumor markers alone cannot be used to assess response. If markers are initially above the upper normal limit, they must normalize for a patient to be considered in complete clinical response.

#### 10.3.6 Cytology, Histology

The cytological confirmation of the neoplastic origin of any effusion that appears or worsens during treatment when the measurable tumor has met criteria for response or stable disease is mandatory to differentiate between response or stable disease (an effusion may be a side effect of the treatment) and progressive disease.

#### 10.3.7 FDG-PET

While FDG-PET response assessments need additional study, it is sometimes reasonable to incorporate the use of FDG-PET scanning to complement CT scanning in assessment of progression (particularly possible 'new' disease). New lesions on the basis of FDG-PET imaging can be identified according to the following algorithm:

- Negative FDG-PET at baseline, with a positive FDG-PET at follow-up is a sign of PD based on a new lesion.
- No FDG-PET at baseline and a positive FDG-PET at follow-up: If the positive FDG-PET at follow-up corresponds to a new site of disease confirmed by CT, this is PD. If the positive FDG-PET at follow-up is not confirmed as a new site of disease on CT, additional follow-up CT scans are needed to determine if there is truly progression occurring at that site (if so, the date of PD will be the date of the

initial abnormal FDG-PET scan). If the positive FDG-PET at follow-up corresponds to a pre-existing site of disease on CT that is not progressing on the basis of the anatomic images, this is not PD.

Note: A 'positive' FDG-PET scan lesion means one which is FDG avid with an uptake greater than twice that of the surrounding tissue on the attenuation corrected image.

#### ***10.4 Response Criteria***

##### 10.4.1. Evaluation of Target Lesions

Complete Response (CR): Disappearance of all target lesions. Any pathological lymph nodes (whether target or non-target) must have reduction in short axis to <10 mm.

Partial Response (PR): At least a 30% decrease in the sum of the diameters of target lesions, taking as reference the baseline sum diameters

Progressive Disease (PD): At least a 20% increase in the sum of the diameters of target lesions, taking as reference the smallest sum on study (this includes the baseline sum if that is the smallest on study). In addition to the relative increase of 20%, the sum must also demonstrate an absolute increase of at least 5 mm. (Note: the appearance of one or more new lesions is also considered progressions).

Stable Disease (SD): Neither sufficient shrinkage to qualify for PR nor sufficient increase to qualify for PD, taking as reference the smallest sum diameters while on study

##### 10.4.2 Evaluation of Non-Target Lesions

Complete Response (CR): Disappearance of all non-target lesions and normalization of tumor marker level. All lymph nodes must be non-pathological in size (<10 mm short axis)

Note: If tumor markers are initially above the upper normal limit, they must normalize for a patient to be considered in complete clinical response.

Non-CR/Non-PD: Persistence of one or more non-target lesion(s) and/or maintenance of tumor marker level above the normal limits

Progressive Disease (PD): Appearance of one or more new lesions and/or unequivocal progression of existing non-target lesions. Unequivocal progression should not normally trump target lesion status. It must be representative of overall disease status change, not a single lesion increase.

Although a clear progression of “non-target” lesions only is exceptional, the opinion of the treating physician should prevail in such circumstances, and the progression status should be confirmed at a later time by the review panel (or Principal Investigator).

#### 10.4.3 Evaluation of Best Overall Response

The best overall response is the best response recorded from the start of the treatment until disease progression/recurrence (taking as reference for progressive disease the smallest measurements recorded since the treatment started). The patient's best response assignment will depend on the achievement of both measurement and confirmation criteria.

**Table 12: Evaluation of Patients with Measurable Disease**

Target Lesions	Non-Target Lesions	New Lesions	Overall Response	Best Overall Response when Confirmation is Required*
CR	CR	No	CR	>4 wks. Confirmation**
CR	Non- CR/Non-PD	No	PR	>4 wks. Confirmation**
CR	Not evaluated	No	PR	
PR	Non- CR/Non-PD/not evaluated	No	PR	
SD	Non- CR/Non-PD/not evaluated	No	SD	documented at least once >4 wks. from baseline**
PD	Any	Yes or No	PD	no prior SD, PR or CR
Any	PD***	Yes or No	PD	
Any	Any	Yes	PD	

\* See RECIST 1.1 manuscript for further details on what is evidence of a new lesion. \*\* Only for non-randomized trials with response as primary endpoint.\*\*\* In exceptional circumstances, unequivocal progression in non-target lesions may be accepted as disease progression.  
Note: Patients with a global deterioration of health status requiring discontinuation of treatment without objective evidence of disease progression at that time should be reported as “symptomatic deterioration.” Every effort should be made to document the objective progression even after discontinuation of treatment.

**Table 13: Evaluation of Patients with Non-Measurable Disease**

Non-Target Lesions	New Lesions	Overall Response
CR	No	CR
Non-CR/non-PD	No	Non-CR/non-PD*
Not all evaluated	No	not evaluated
Unequivocal PD	Yes or No	PD
Any	Yes	PD
* 'Non-CR/non-PD' is preferred over 'stable disease' for non-target disease since SD is increasingly used as an endpoint for assessment of efficacy in some trials so to assign this category when no lesions can be measured is not advised		

#### 10.4.3 Duration of Response

Duration of overall response: The duration of overall response is measured from the time measurement criteria are met for CR or PR (whichever is first recorded) until the first date that recurrent or progressive disease is objectively documented (taking as reference for progressive disease the smallest measurements recorded since the treatment started). The duration of overall CR is measured from the time measurement criteria are first met for CR until the first date that progressive disease is objectively documented.

Duration of stable disease: Stable disease is measured from the start of the treatment until the criteria for progression are met, taking as reference the smallest measurements recorded since the treatment started, including the baseline measurements.

## 11.0 ETHICAL CONSIDERATIONS

This study is to be conducted according to US and international standards of Good Clinical Practice (FDA Title 21 part 312 and International Conference on Harmonization guidelines), applicable government regulations and Institutional research policies and procedures.

This protocol and any amendments will be submitted to a properly constituted independent Ethics Committee (EC) or Institutional Review Board (IRB), in agreement with local legal prescriptions, for formal approval of the study conduct. The decision of

the EC/IRB concerning the conduct of the study will be made in writing to the investigator and a copy of this decision will be provided to the sponsor before commencement of this study. The investigator should provide a list of EC/IRB members and their affiliate to the sponsor.

All subjects for this study will be provided a consent form describing this study and providing sufficient information for subjects to make an informed decision about their participation in this study. This consent form will be submitted with the protocol for review and approval by the EC/IRB for the study. The formal consent of a subject, using the EC/IRB-approved consent form, must be obtained before that subject is submitted to any study procedure. This consent form must be signed by the subject or legally acceptable surrogate, and the investigator- designated research professional obtaining the consent.

**Appendix A: Schedule of Events**

Pre-study evaluations including scans are to be conducted within 28 days prior to start of protocol therapy. Laboratory assessments are to be done within 5 days of scheduled date. If correlative biopsies are not obtained due to lack of funding, these omissions will not be considered protocol deviations.

	Pre-Study	Cycle 1 (28 days)			Cycle 2 (28 days)		Cycle 3 and later cycles (28 days)
		Day 1	Day 2	Day 15	Day 1	Day 15	Day 1
Office Visit 	X	X		X	X		X
Treatment							
HCQ A		X-----X					
Regorafenib B		X-----X					
Entinostat C		X-----X					
Tests and Observations							
Informed consent	X						
Inclusion/exclusion criteria	X						
Demographics	X						
Medical history	X						
Concurrent meds	X	X		X	X		X
Physical exam 	X	X		X	X		X
Vital signs 	X	X		X	X		X
Height	X						
Weight	X	X		X	X		X
Performance status	X	X		X	X		X
Adverse event evaluation		X		X	X		X
Laboratory Studies							
Complete blood count with differential 	X	X		X	X	X	X
PT/aPTT 	X						
Chemistry profile 	X	X		X	X		X
CEA 	X	X			X		X
Urine or Serum B-HCG (women of childbearing potential) 	X	X 					
Radiologic Evaluations							
CT/MRI 	X						X
Research Correlates							
PBMCs for PD Analysis 		X	X	X			
Tumor Biopsies 				X			

A: HCQ will be administered according to Section 4.2 (days 1-28). See Section 5.0 for dose modifications.

B: Regorafenib will be administered at 160 mg (Days 1-21), unless adjusted as per Section 4.1. See Section 5.0 for dose modifications.

C: Entinostat will be administered according to Section 4.2 (Days 1, 8, 15, 22). See Section 5.0 for dose modifications.

1: The pre-study visit must be within 28 days of starting therapy (Cycle 1 Day 1). Office visits should occur within 1 week of the originally scheduled date. Longer delays should be discussed with the principal investigator.

2: Complete physical exam will be completed at baseline; focused physical examinations will be conducted thereafter.

3: Blood pressure, heart rate, oxygen saturation, temperature

4: After Cycle 2, done Day 1 of each cycle, provided that hematologic toxicity is tolerable. Patients on non-prophylactic anticoagulation must have CBC weekly for cycles 1 and 2 and every 2 weeks with subsequent cycles.

5: Screening or Cycle 1 Day 1 only.

6: Na, K, Ca, Mg, phosphorus, BUN, creatinine, glucose, alkaline phosphatase, AST, ALT, total bilirubin, albumin, total protein. After Cycle 1, done Day 1 of each cycle unless concerning toxicity

7: CEA will be checked at baseline. If it is elevated, it will be checked on day 1 of each cycle, otherwise it will not be routinely followed.

8: Serum B-HCG will be checked at screening and either urine or serum B-HCG must be checked within 3 days of initiation of study drug

9: Radiologic evaluations (CT preferred, MRI acceptable; PET/CT only if required per treating physician) of the abdomen/pelvis and chest (if thoracic disease is present) and tumor measurements will be performed at baseline (within 4 weeks of study therapy), at Cycle 3 Day 1 and Cycle 5 Day 1 (or within 2 weeks), then every 8-12 weeks per standard practice. Scans may be evaluated for texture analysis as a baseline for exploratory radiomic endpoints.

10: Sample handling as in Laboratory Manual.

11: Tumor biopsies to be taken in phase II portion (when funding obtained) in subjects who meet eligibility at Cycle 1 between day 15 and day 22 if possible. Archived tumor material prior to treatment will also be analyzed, as discussed in section 4.9.

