### ***4.1 Regorafenib Dosing***

All patients will receive regorafenib at the FDA-approved dose of 160 mg by mouth daily for days 1-21 of a 28-day cycle. As noted below, dose decreases of regorafenib are often required in the initial cycle, followed by tolerance of full doses in subsequent cycles: such manipulations of the regorafenib dose are standard, and will not be taken into account in determining the MTD. Should excess toxicity attributable to regorafenib be repeatedly observed, the principal investigator may institute a standard initial dose escalation period. This will consist of regorafenib 80mg daily for the first 7 days of therapy, followed by increase to 120 mg for days 8-14 if 80mg tolerated, and 160 mg for days 15 and beyond if 120 mg tolerated.

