#### ***4.8 Laboratory Testing***

Patients will have laboratory testing at the pre-treatment screening visit, cycle 1 day 1, and cycle 1 day 15 as described in the schedule of events (Appendix A), including complete blood count with differential and comprehensive metabolic panel with magnesium and phosphorous. Complete blood counts will be continued every two weeks until week 8, and then every four weeks if the hematologic toxicity is tolerable. Comprehensive metabolic panel, magnesium, and phosphorous will be checked every 4 weeks after the initial testing unless there is concerning toxicity. CEA will be checked at baseline, and, if it is elevated above the laboratory upper limit of normal, will be checked on day 1 of each 28-day cycle. Prothrombin time (PT) and activated prothromboplastin time (aPTT) will be checked at baseline. Patients on non-prophylactic anticoagulation will have a complete blood count weekly for cycles 1 and 2, and every 2 weeks with subsequent cycles.

For correlative pharmacodynamic testing, blood samples for peripheral blood mononuclear cells (PBMCs) will be obtained on cycle 1 day 1 (prior to therapy administration), cycle 1 day 2, and cycle 1 day 15. As in our previous study, autophagy inhibition will be assessed using western analysis of autophagy markers in PBMCs. HDAC inhibition will be measured through multiparametric flow cytometric analysis of histone and non-histone targets of de-acetylation enzymes in PBMCs in collaboration with [name], NIH. In addition, the effects of the treatment on lymphocyte subsets will be analyzed by flow cytometry. The procedures for this are further described in the laboratory manual.

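### Between Cycle 2 Day 1 and Cycle 3 Day 1 no liver chemistry or blood pressure is scheduled, so the regorafenib rules in 5.1 have no mid-cycle 2 reading to act on

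*Combined protocol and SAP*

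**What the plan says.** - **Dosing.** Section 4.1 gives regorafenib "160 mg by mouth daily for days 1-21 of a 28-day cycle".
- **Chemistry.** The Appendix A grid marks the panel at pre-study, C1D1, C1D15, C2D1 and Day 1 of cycle 3 and later. It is blank at C2D15. Footnote 6 agrees: "After Cycle 1, done Day 1 of each cycle unless concerning toxicity".
- **Section 4.8** is looser: "Comprehensive metabolic panel, magnesium, and phosphorous will be checked every 4 weeks after the initial testing unless there is concerning toxicity". It does not name the day from which the four weeks run.
- **Blood count.** This is the only test marked at C2D15, in line with Section 4.8: "Complete blood counts will be continued every two weeks until week 8".
- **Blood pressure.** It appears only in the vital signs row, defined in footnote 3 as "Blood pressure, heart rate, oxygen saturation, temperature". That row is also blank at C2D15, as are the office visit, physical examination and adverse event rows.
- **Windows.** "Laboratory assessments are to be done within 5 days of scheduled date"; "Office visits should occur within 1 week of the originally scheduled date".
- **Rules that need a reading.** Section 5.1 interrupts regorafenib for symptomatic grade 2 hypertension and for any attributable grade 3 or 4 reaction. It reduces the dose for grade 3 AST or ALT. It stops the drug for good if AST or ALT passes 20 × ULN, or passes 3 × ULN while bilirubin is above 2 × ULN. It sets no monitoring schedule of its own.

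**The concern.** The 5.1 rules can act only on something that has been measured. In cycle 2 the two scheduled readings sit at either end of the dosing period: one at its start, after a week off drug, and one after it has finished. A new abnormality that causes no symptoms in between has nothing scheduled to reveal it. If it settles before C3D1 it is never seen, although a single occurrence of the combined AST/ALT and bilirubin criterion is meant to end treatment. If it persists, it is seen only after the patient has taken the whole course.

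The stake is patient safety. Under 3.1.12, patients with liver metastases may enter with AST or ALT up to 5 × ULN. Some may therefore already exceed the 3 × ULN half of the stop rule, and a silent bilirubin rise alone would complete it. Section 2.5 reports grade 3-4 hypertension of 7% and 11% in the two phase III regorafenib trials. In the second trial it reports bilirubin, ALT and AST abnormalities of 7%, 7% and 6%.

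**Working it through.** The plan states no figure to reproduce; the check is a count of days.

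**Inputs.** 28-day cycles with regorafenib on days 1-21 (4.1). Laboratory window ±5 days and visit window ±7 days (Appendix A). I assume that vital signs follow the visit window and that dosing starts on time. In study days, C2D1 = 29, C2D15 = 43, C2D21 = 49 and C3D1 = 57.

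**1. Nominal gap.** From the last cycle 2 dose to the next reading: 57 − 49 = 8 days.

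**2. Gap with windows fully used.**

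| | Chemistry (±5) | Blood pressure (±7) |
|---|---|---|
| Latest C2D1 reading | 29 + 5 = day 34 (C2D6) | 29 + 7 = day 36 (C2D8) |
| Earliest C3D1 reading | 57 − 5 = day 52 | 57 − 7 = day 50 |
| Dosing days never covered | days 35-49 (C2D7-C2D21) | days 37-49 (C2D9-C2D21) |
| Share of 21 | 15/21 = 71% | 13/21 = 62% |
| Earliest C3D1 reading after last dose | 52 − 49 = 3 days | 50 − 49 = 1 day |

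A late C2D1 reading can thus follow up to 6 doses (chemistry) or 8 doses (blood pressure). No permitted timing places a reading in the last 13 dosing days.

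**3. What a C2D15 panel adds.** Its window is days 38-48, that is C2D10-C2D20, always a dosing day. The nominal chemistry interval falls from 28 to 14 days. The widest interval falls from 62 − 24 = 38 days to 48 − 24 = 24 days (and likewise 62 − 38 = 24).

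**4. Doses a hold could spare, if acted on the same day.**
- Drawn on C2D10 before that day's dose: doses 10-21, so 12.
- Drawn on C2D15: 7 (before the dose) or 6 (after it).
- Drawn on C2D20 after the dose: 1.
- First seen at C3D1: 0.

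**5. Section 4.8.** Counted from C1D15, four weeks later is day 15 + 28 = 43, which is C2D15. Counted from C1D1, it is C2D1. The text supports either; footnote 6 supports only Day 1. Neither reading adds a blood pressure check.

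**6. Effect on the recommended phase II dose.** The 4.3 regorafenib criterion is 80% of 21 × 160 = 3360 mg, or 2688 mg, for a patient who starts cycle 2 at 160 mg. With no reading and no hold, the patient scores 100%. With a hold after the Day 15 dose, *k* missed days and resumption at 120 mg, the share is (15 × 160 + (6 − *k*) × 120)/3360. For *k* = 3 this is 2760/3360 = 82.1% (passes); for *k* = 4 it is 2640/3360 = 78.6% (fails).

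Tolerability needs 4 of 6 patients, so it fails if 3 or more fail. Suppose every event at the single-agent rate were silent, fell in cycle 2 and failed the criterion. Then P(X ≥ 3) with n = 6 is 0.6% at *p* = 7%, 2.1% at 11% and 7.6% at 18%. The last adds 11% hypertension to 7% liver as separate patients and treats the three liver rates as overlapping.

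**The case against.** The strongest reply is that 15 or 13 uncovered days do not measure missed events. A miss needs an abnormality that is new after C2D1, silent, severe enough to trigger 5.1, and gone by C3D1. That frequency is not in the documents. This stands, and the day counts should not be read as a miss rate.

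Other safeguards exist. Extra chemistry is allowed for concerning toxicity, 8.5 requires questioning at each contact, and 8.3 contemplates closer follow-up of abnormal values. Sections 3.2.1(b) and 3.2.8 keep out uncontrolled hypertension. The only hypertension-specific trigger in 5.1 requires symptoms, which a patient can report. These catch symptomatic or already known problems; none detects a new silent rise.

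Section 4.1 says "dose decreases of regorafenib are often required in the initial cycle, followed by tolerance of full doses in subsequent cycles", which puts the main risk in cycle 1, where C1D15 gives an on-drug reading. That is fair. It also means some patients may return to 160 mg in cycle 2, although 5.0 normally keeps reductions in place.

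The C3D1 reading is not always clear of drug. At 1 to 3 days after the last dose and a half-life of 20-40 hours (2.5), some exposure remains. This stands too, but such a reading still comes after the 21st dose.

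Finally, testing stays on Day 1 from cycle 3 onward, so one added panel does not answer the principle in full. True. Cycle 2 is singled out because blood is already being drawn mid-cycle for every patient; later, only patients on non-prophylactic anticoagulation have such a draw.

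**Conclusion.** The point holds as a cheap patient-safety improvement. After C2D1 the plan schedules no liver chemistry or blood pressure until after the last cycle 2 regorafenib dose, whichever permitted dates are used. A new silent event in that span is missed if it resolves, or acted on only after 21 doses. For an affected patient, a C2D15 panel could spare 1 to 12 doses (6 or 7 if drawn on Day 15), provided the result is acted on the same day. The number of such patients cannot be computed.

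A reader might infer more, and the documents do not support it:
- *That the recommended phase II dose is unsafe or biased.* The probabilities above are small even though they assume every event is silent, in cycle 2 and disqualifying. They rest on all-cycle single-agent rates, since none is given for the combination. Failing 4.3 would also lower HCQ or entinostat, not regorafenib. I regard the effect as negligible.
- *That the C2D1 reading shows at most one dose.* That is so only on nominal dates.
- *That patients go unmonitored.* Symptomatic and persistent events are still found.

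**What to change.** 1. Appendix A: mark the chemistry row at C2D15, using the blood already drawn for the count.
2. Footnote 6: state that from cycle 2 the panel is done on Day 1 of every cycle and also on Cycle 2 Day 15, and more often where toxicity is a concern.
3. Section 4.8: replace the four-weekly phrase with the same wording, so that text and grid give one schedule.
4. Secondary: add a blood pressure reading at that draw. C2D15 is not an office visit, so the site must name who takes the reading and who acts on both results.

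No added testing is asked from cycle 3 onward.

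**Cost.** One extra panel per patient, plus a brief pressure check if item 4 is adopted. Reported liver abnormality rates or 4.3 failures may rise slightly, and a hold of regorafenib alone could count towards lowering HCQ or entinostat.
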